7. The radiographic examination will be performed by taking periapical x-ray using (parallel technique) through machine to assess the inclusion criteria. The preoperative radiograph will serve as a reference for the follow-up radiographs. Standardization of the technique to avoid any distortion in the vertical dimension and to provide reproducible images using x-ray holding device.
8. Preoperative and postoperative radiograph will be taken by parallel technique using XCP film holder (Super Bite, Hawe Neos Dental SA, Switzerland).
9. Administration of inferior alveolar nerve block (Septodont, Scandonest® 2% L Mepivacaine HCl. 2% and Levonordefrin 1:20,000 Injection, U.S.P.) at the side of the affected tooth.
10. Application of rubber dam for isolation, then a standardized pulpotomy procedure will be performed using a large sterile round end bur in a high-speed handpiece with copious irrigation, a sharp spoon excavator will remove pulpal tissues to the orifice level. Hemostasis will be achieved by the application of a wet cotton pellet to achieve complete hemostasis.
11. Children will then be allocated into either one of the groups alternatively depending on the pulpotomy medicament used as follows:
Group I (Experimental group) collagen based pulpotomy.
Group II (Control group) Biodentine pulpotomy.

Group I (Experimental group) collagen based Pulpotomy:

1. Collagen based pulpotomy will be applied (sterile medicated collagen particles, Biofil-AB, Eucare Pharmaceuticals Pvt. Ltd, Chennai, India) according to the manufacturer's instructions and gently placed over the pulp stumps to a thickness of 2 mm.

Group II (Control group) Biodentine pulpotomy:

1. Biodentine (Septodont, Saint-Maur-des-Fossés, France) will be applied according to the manufacturer's instructions and placed over the radicular pulp with the help of a suitable sterile amalgam carrier. Gentle condensation of the mix will be done in the pulp chamber with a moistened cotton pellet.

12. For both groups;

The rest of the pulp chamber will be filled with glass ionomer cement.

Tooth will then be restored with stainless steel crown (3M ESPE, St Paul, MN, U.S.A.).

12. Outcomes:

Primary outcome:

Absence of periapical radiolucency and internal/ external root resorption (Binary outcome detected with periapical x-ray by Parallel technique using XCP film holder (Super Bite, Hawe Neos DentalSA, Switzerland).

Secondary outcome:

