1- Survival rate (absence of any complication or complementary treatment) in terms of:

1-Absence of spontaneous pain. (Binary outcome measured with direct questioning to the patient).

2-Absence of swelling. (Binary outcome measured visually by intraoral/extraoral examination).

2- Time elapsed till final restoration performed.

13. Participant timeline:

Patients will be diagnosed to determine whether they are eligible for the inclusion criteria of this study or not.

Eligible patients will then start their treatment on the same visit.

	STUDY PERIOD					
	Enrolment	Allocation	Treatment visit	Post-treatment	Close-out	
TIMEPOINT	-t1	0	0	T1 (3m)	T2 (6m)	
ENROLMENT:						
Eligibility screen and patient selection	X					
Informed consent from participating pts	X					
Allocation (concealed in closed white envelop)	X					
INTERVENTIONS:						
The pulpotomy procedure (gaining access to the pulp)		X				
Allocation of the patient to one of the treatments groups (open the closed white envelope)		X				
Application of pulp dressing material (collagen and Biodentine)			X			
Final restoration			X			
ASSESSMENTS:						
baseline variables	1- photographs	X		X	X	X
	2- percussion test	X		X	X	X

	3- preoperative periapical radiograph	X				
	4- personal data	X				
outcome variables	Calculation of time-elapsed till final restoration			X		
	Questioning the patient about the absence of spontaneous pain	X			X	X
	Visual examination of patient to check the absence of sinus or Swelling	X			X	X
	Periapical radiograph to check the absence of periapical radiolucency, internal/ external root resorption	X		X	X	X

14. Sample size:

Sample size will be calculated.

15. Recruitment:

Patients attending the out-patient clinic in the pediatric dentistry department- Cairo University, having bilateral carious lower molars will be carefully assessed for eligibility to participate in our study by one of the main investigators [name], then a full explanation of the nature of our experiment and the importance of maintaining this primary tooth and restoring it for proper functions and the drawbacks of extracting it. Full mouth treatment will be offered for them.

B) Assignment of interventions:

16. Allocation:

16a. Random sequence generation (Randomization):

Teeth that will be included in the current trial will be randomly assigned one of the experimental groups using closed white envelopes (simple randomization 1:1 ratio).

a) Sequence generation:

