By shuffling the envelopes then selecting envelop for each patient upon their enrolment.

b) Allocation Concealment:

Using 8-time folded paper on which dressing material was written contained in the closed white envelope.

c) Implementation:

When a patient agrees to participate in the trial, an envelope will be drawn by one of the residents present at the clinic and name, telephone number and patient's ID will be written on it. Those selected envelopes will be opened at treatment visit after performing pulpotomy to choose which material should be used.

Randomization and allocation concealment will be performed by the co-supervisor to avoid selection bias.

17. Blinding:

The blinding is not possible (unfortunately) due to the nature of the trial.

Trial participants, outcome assessors and statistician will be blinded.

C)Data collection, management, and analysis:

18. Data collection methods

Baseline data collection

Plans for assessment and collection of outcomes will be at 3 and 6 months clinically (using visual examination, palpation, and percussion test with back of the mirror) and 0 and 6 months radiographically (using periapical radiograph) and will be done by two blinded assessors independently, and differences will be solved by consensus. To promote data quality, duplicate measurements by the same examiner (intra-examiner agreement) and training of assessors (inter-examiner agreement) will be done.

19. Data management:

Data will be recorded on a diagnostic chart for each patient separately and will be stored with follow up periapical radiographs.

20. Statistical methods:

Clinical and radiographic outcomes will be submitted for statistical analysis by the Statistical Package for Social Science (SPSS) program windows version 13. Results will be calculated using risk reduction (R.R.).

D) Data monitoring:

21. Monitoring

The study work results will be monitored regularly by the supervisors who will have full access to these interim results make the final decision to terminate the trial.

22. Harms

- **Bur breakage:** the bur will be replaced by a new one and treatment will be proceeded.
- **Perforation of pulpal wall or floor:** The tooth condition and size of perforation will be assessed whether the treatment will be to repair the perforation and treatment will be proceeded (the tooth will be removed from the trial) or the tooth will be extracted, and space maintainer will be performed

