The investigator will be given access to data sets. All data sets will be password protected. To ensure confidentiality, data dispersed to project team members will be blinded of any identifying participant information.

30. post-trial care:

The investigator will offer full mouth treatment, post-operative care, and preventive measures to all participants.

31. Dissemination policy:

The Thesis defense will be done as the study is a part of the requirements for a master's degree in Pediatric Dentistry. Also, the results of the study will be published in Journals.

V. Appendices**Appendix 1: Chart filled for each patient in this trial:**

Patient name:

Patient ID:

Tested material:

Age:

sex:

Address:

Telephone:

Chief complain of the patient:

Pretreatment medications:

Participating tooth:

Date of material application:

Follow up		1ry outcomes assessment clinical assessment (survival rate)		2ry outcomes assessment Radiographic assessment			Final assessment “success or failure”
Time after	Date	1- Spontaneous pain	2- Swelling	3- Internal root resorption	4 - External root resorption	5- Periapical radiolucency	
3m	/ /20						
6m	/ /20						

VI. References:

- 1- izGuven SD. *Success Rates of Pulpotomies in Primary Molars Using Calcium SilicateBased Materials: A Randomized Control Trial. Biomed Res Int.* 2017;2017:7.
- 3- *Use of collagen as a biomaterial: An update - researchgate. (n.d.). Retrieved March 6, 2022, from* https://www.researchgate.net/publication/258204888_Use_of_collagen_as_a_biomaterial_An_update
- 5- J. Camilleri. “Hydration characteristics of biodentine and theracal used as pulp capping materials.” *Dent Mater.* 2014;30:709–715.

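### Sections 13 and 18 disagree on whether a 3-month radiograph is taken for the primary outcome, and Section 12 names no time point for that outcome

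*Protocol*

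**What the plan says.** Four places in the protocol bear on when the primary outcome is read.

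- **Section 12** defines the primary outcome as "Absence of periapical radiolucency and internal/ external root resorption", a binary finding on a periapical film. It gives no month. Section 7 gives an overall follow-up of 6 months.
- **Section 13** has a timeline row for this outcome, "Periapical radiograph to check the absence of periapical radiolucency, internal/ external root resorption". It is marked at enrolment, at the treatment visit, at T1 (3 months) and at T2 (6 months, the close-out visit).
- **Section 18** gives two schedules in one sentence. The clinical one is "Plans for assessment and collection of outcomes will be at 3 and 6 months clinically". The radiographic one is "0 and 6 months radiographically (using periapical radiograph").
- **Appendix 1** is the chart kept for each patient. It has a 3-month and a 6-month row. Each has columns for internal resorption ("3- Internal root resorption"), external resorption and periapical radiolucency, and each ends in a final success-or-failure entry.

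Section 22 adds that a tooth whose pulpotomy fails is retreated and taken out of the trial.

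**The concern.** Staff cannot follow Section 13 and Section 18 together. One calls for a film at 3 months and the other leaves it out, and the film in question is the one on which the primary outcome is read.

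Three things depend on the answer:

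- **Exposure.** The number of radiographs per child, in children aged 4 to 7, differs between passages that the ethics committee reviews together.
- **Number of readings.** The primary outcome has either one or two follow-up readings, and Section 12 does not say which of two would be primary.
- **When a failure can be called.** With a 3-month film, a failure visible only on the radiograph could be declared at 3 months. Without it, such a failure is first read at 6 months. Because Section 22 removes failed teeth, the schedule may affect which teeth still have a 6-month reading. In this split-mouth design, losing one tooth also breaks that child's pair.

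**Working it through.** The protocol states no figure on this point, so there is nothing to reproduce. The check sets the schedules side by side and counts films.

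| Place | Month 0 | 3 months | 6 months |
|---|---|---|---|
| Section 13, outcome radiograph | enrolment and treatment visit | yes | yes |
| Section 18, radiographic | yes (one or two films) | no | yes |
| Section 18, clinical | not listed | yes | yes |
| Appendix 1, radiographic columns | no row | yes | yes |

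**Is the gap real?** Section 18 contrasts clinical and radiographic times within one sentence, so the missing 3-month film is not shorthand for all follow-up visits. A misaligned table does not explain it either: in the same timeline the pain and swelling rows are marked at 3 and 6 months, which matches Section 18's clinical schedule. The month-0 film is not in dispute between Sections 13 and 18; it is absent only from the chart.

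**Films per tooth.** The separate row "3- preoperative periapical radiograph" is marked at enrolment only. I take it to be the same film as the enrolment mark in the outcome row.

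- Section 13: enrolment + treatment visit + 3 months + 6 months = 4.
- Section 18, month 0 covering a film before and a film after treatment: 2 + 1 = 3. Section 11 supports this reading: "Preoperative and postoperative radiograph will be taken by parallel technique using XCP film holder".
- Section 18, month 0 as a single film: 1 + 1 = 2.
- Difference: 4 − 3 = 1, or 4 − 2 = 2.

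With two study teeth per child, each filmed separately, that is 8 films against 6 or 4, a difference of 2 or 4 per child.

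**Follow-up readings of the primary outcome per tooth.** Section 13 and the chart give 2 (3 and 6 months). Section 18 gives 1 (6 months).

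**Effect of early removal, if removed teeth are left out.** In one arm of *n* teeth, let *a* be declared failures at 3 months and removed, and let *b* more fail by 6 months.

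- Removed teeth counted as failures: rate = (*a* + *b*)/*n*.
- Removed teeth left out: rate = *b*/(*n* − *a*).
- First minus second = *a*(*n* − *a* − *b*) / [*n*(*n* − *a*)], which is never negative.

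Leaving removed teeth out can therefore only lower the observed failure rate or leave it unchanged. The size depends on *a*, *b* and *n*. The protocol gives none of these, so no figure is put on it.

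**The case against.** Several objections have weight.

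- **There are no rival primary time points.** A reader might infer that the passages name two different primary time points. They do not. Section 7 states 6 months, Section 13 labels the 6-month visit close-out, and the 6-month film is common to Section 13, Section 18 and the chart. What conflicts is the 3-month film. The primary time point is only unnamed in Section 12. This objection stands in full.
- **Inflated type I error.** A reader might infer that two readings let success be claimed at whichever visit is favourable, with a calculable rise in false positives. The protocol states no significance level, no test and no rule allowing a claim at either visit, and multiplicity is commonly settled in the statistical analysis plan, which is not at hand. Any error rate would be a property of assumptions brought from outside, so none is given.
- **Section 22 does not define failure.** It lists failure under harms without tying it to a radiographic finding. Removal after a radiographic failure at 3 months is a natural reading alongside the chart's 3-month success-or-failure entry, but it is not an explicit rule. Teeth that fail clinically at 3 months could also be removed under either film schedule, so the schedule alone does not decide who reaches 6 months. The mechanism is therefore stated here as conditional.
- **The chart is a blank grid.** An empty cell does not order a film. Appendix 1 therefore corroborates the 3-month reading but does not establish it; the conflict rests mainly on Section 13 against Section 18.

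None of these removes the contradiction between those two sections.

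**Conclusion.** The point holds as an internal inconsistency. Section 13, supported by Appendix 1, has a 3-month radiograph for the primary outcome, and Section 18 does not. The difference is one film per tooth, or two if month 0 in Section 18 means a single film, and one against two follow-up readings of the primary outcome. The count assumes that the two enrolment marks in the timeline are one film; the per-child figures also assume that each study tooth is filmed separately.

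The missing time point in Section 12 is a smaller gap, because 6 months is clearly the intended end of follow-up. The loss of 6-month readings through Section 22 is possible rather than certain: it depends on the chart's 3-month call counting as failure under that section. It should be corrected before enrolment because the schedule governs films taken from the first child on.

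The chart also files these findings under "2ry outcomes assessment Radiographic assessment", although Section 12 makes them primary. That is a separate inconsistency and is not needed for this point.

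**What to change.** 1. Reconcile Section 13, Section 18 and Appendix 1 on whether a 3-month radiograph is taken. This review does not say which schedule is right. In Section 18, also say whether month 0 means one film or a film both before and after treatment.
2. In Section 12, state that the 6-month reading is the time point for the primary outcome and that any 3-month reading is secondary.
3. In Section 12, also state that a tooth declared a failure before 6 months and removed under Section 22 counts as a failure in the 6-month primary analysis. This concerns counting only and leaves the management in Section 22 as it is.

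The cost is wording in Sections 12, 13, 18 and Appendix 1. No visit is added, since a 3-month clinical visit is already planned. Whether a film is added or dropped, relative to any one passage, depends on how the first item is settled.

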	3- Time elapsed till final restoration performed	Stopwatch	Continuous outcome measured in minutes

(S) Study design: Randomized controlled.

(T) Time of follow up:6 months.

8. Trial design:

Randomized controlled trial (R.C.T).

III. Methods

A) Participants, interventions & outcomes:

9. Study settings:

This study will be carried out on patients attending the out-patient clinic in Pediatric Dentistry and Dental Public Health Department-faculty of Dentistry, Cairo University, Egypt.

The procedure will be carried out by postgraduate student [name], B.D.S(2014)-Pharos University in Alexandria (PUA) and without an assistant.

10. Eligibility criteria:

Inclusion criteria:

- Children:

- 1- Aged 4 to 7, in good general health and medically free.
- 2- Cooperative patients who will comply to follow ups.
- 3- Parents provided with written informed consent.

- Teeth:

- 1- Bilaterally Carious vital primary molars with reversible pulpitis.
- 2- Restorable teeth with no more than 1/3 of root resorption.

Exclusion criteria:

- Children:

- 1- Children with medical, physical, or mental conditions.
- 2- Unable to attend follow up visits.

- Teeth:

- 1- Primary molars with any congenital anomalies.
- 2- Previously accessed teeth.
- 3- At operative procedure, haemorrhage control is unachievable after pulpotomy.

11. Interventions

The principal investigator will carry out all treatment procedures, using the split mouth technique, meaning that both groups (I & II) will be in the same patient.

For both interventions:

1. Informed consent from participating parents.
2. Baseline records photographs, percussion test, periapical radiograph, and personal data collection (Appendix 1: Diagnostic chart).
3. Allocation (concealed by withdrawing a sealed opaque envelope containing eight times folded paper containing the type of dressing material that will be used then writing patient name and ID on it and will be opened after performing the access cavity).
4. Diagnostic chart with personal, medical, and dental history will be filled (Appendix 1: Diagnostic chart).
5. Clinical examination will be performed to assess the clinical inclusion criteria. (Pulpal and periapical diagnosis is established after clinical examination).
6. Preoperative and Postoperative photographs will be taken.

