- **No reported hypersensitivity from both tested materials.**
- **Failure of pulpotomy procedure:** retreatment of the tooth through partial pulpectomy and tooth will be removed from the trial.

23. Auditing

The study supervisors will regularly assess the trial process and documents. They will be involved in participant enrolment, consent, eligibility and allocation to study groups, adherence to trial interventions and policies to protect participants, including reporting of complications and their treatments. Clinical procedures will be performed under their supervision.

IV. Ethics and dissemination

24. Research ethics approval:

This protocol, the template and specific informed consent forms (local language and English versions) will be reviewed, approved, and agreed upon by the (Research Ethics Committee) will review all the nature of interventions and will have the right to modify the study methods.

25. Protocol amendments:

The Ethics Committee will be notified of any administrative changes or modifications of the protocol. Any required changes during the trial period for the patient's own interest that might affect the conduct of the study, including changes of the study objectives, study design, patient population, sample sizes, intervention procedures will require a formal amendment to the protocol. Such amendment will be agreed upon by the Council of the Department of Pediatric Dentistry, Faculty of Dentistry, Cairo University.

26. Informed consent:

The investigator will discuss the trial with the legal guardian of each participating child:

- Verbal permission will be taken orally from participating child.
- Written informed consent will be taken from the legal guardian of each participating child willing to participate in the trial. The consent form will be written in Arabic.

27. Confidentiality:

All data, information, participant's personal information, family history, social and medical history will be stored in the files assigned to each patient with limited access to a minimum number of individuals necessary for quality control, audit, and analysis.

28. Declaration of interest:

This study is a part of a master's degree in Pediatric Dentistry, Faculty of Dentistry, Cairo University. No financial conflict of interests is confirmed. The study is self-funded by the principal investigator.

29. Access to data:

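### A tooth whose pulpotomy fails leaves the trial with no statement that it still counts as a failure, and the one named effect measure and the unit compared are not settled

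*Protocol*

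**What the plan says.** **Removed teeth.** Under failure of the procedure, section 22 (Harms) prescribes "retreatment of the tooth through partial pulpectomy and tooth will be removed from the trial". Section 12 defines a secondary outcome as "Survival rate (absence of any complication or complementary treatment", followed by pain and swelling. The Appendix 1 chart has a success-or-failure column with rows at 3 and 6 months. No sentence says whether a removed tooth stays in the analysis.

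**Visits.** Section 18 schedules assessment "at 3 and 6 months clinically", and radiographically at 0 and 6 months. The section 13 timeline also marks a radiograph at 3 months, and Appendix 1 has radiographic cells in its 3-month row.

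**Effect measure.** Section 20 gives one: "Results will be calculated using risk reduction (R.R", with no statement of absolute or relative and no event. The binary outcomes in sections 7 and 12 are all worded as absences, that is, as successes.

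**Unit.** Section 11 describes treatment "using the split mouth technique, meaning that both groups (I & II) will be in the same patient", and section 16a reads "Teeth that will be included in the current trial will be randomly assigned one of the experimental groups". Section 11, step 11, reads "Children will then be allocated into either one of the groups alternatively", and the timeline has "Allocation of the patient to one of the treatments groups". Section 14 leaves the sample size to be calculated.

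**The concern.** The same tooth is an event under section 12 and gone under section 22. Failure is what the trial counts, so a rule that takes failed teeth out, if followed in the analysis, removes information because of the outcome itself. In a split-mouth design it also costs the partner tooth, since the pair is no longer complete.

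The effect on the result depends on the scale reported, and section 20 leaves that scale open. If the scale and the handling of removed teeth are both undecided when results are seen, they can be chosen with the answer in view. The sample size still to be calculated needs the same decisions, together with the unit.

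**Working it through.** The protocol states no failure rate, correlation or sample size, so there is no figure to reproduce. Steps 1 and 3 compare the text. Step 2 and the figures in step 3 are illustrations on assumed values.

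**Step 1. Which failures could be lost before the 6-month reading?**

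| Source | Clinical follow-up | Radiographs |
|---|---|---|
| Section 18 | 3, 6 months | 0, 6 months |
| Section 13 timeline | 3, 6 months | enrolment, treatment visit, 3, 6 months |
| Appendix 1 | 3, 6 months | 3, 6 months |

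On section 18, only teeth that fail clinically before 6 months would leave before the closing radiograph. On the timeline and Appendix 1, radiographic failures seen at 3 months would leave too. On either schedule, a failure first seen at 6 months is observed at that visit and is not lost.

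**Step 2. Size of the distortion.** Assumed: failure q_B = 0.05 (Biodentine) and q_C = 0.15 (collagen); within-child correlation 0.3; the same share f of failures removed early with each material, independently between teeth.

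Pair probabilities with nothing removed:
- both fail = 0.05×0.15 + 0.3×√(0.05×0.95×0.15×0.85) = 0.0075 + 0.0233 = 0.0308
- Biodentine only fails = 0.05 − 0.0308 = 0.0192
- collagen only fails = 0.15 − 0.0308 = 0.1192
- both succeed = 1 − 0.0308 − 0.0192 − 0.1192 = 0.8308

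Complete pairs after removal: both fail × (1−f)²; each single failure × (1−f); both succeed unchanged.

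| f | both fail | Biodentine only | collagen only | both succeed | pairs kept |
|---|---|---|---|---|---|
| 0 | 0.0308 | 0.0192 | 0.1192 | 0.8308 | 1.000 |
| 0.25 | 0.0174 | 0.0144 | 0.0894 | 0.8308 | 0.952 |
| 0.50 | 0.0077 | 0.0096 | 0.0596 | 0.8308 | 0.908 |

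Difference, collagen minus Biodentine = (collagen only − Biodentine only) / pairs kept:
- f = 0: 0.1000, or 10.0 points
- f = 0.25: 0.0750/0.952 = 7.9 points
- f = 0.50: 0.0500/0.908 = 5.5 points

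Relative risk of failure in the same pairs = (collagen only + both fail) / (Biodentine only + both fail):
- f = 0: 0.15/0.05 = 3.0
- f = 0.25: 0.1068/0.0318 = 3.36
- f = 0.50: 0.0673/0.0173 = 3.89

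The ratio rises because a pair in which both teeth fail must escape removal twice, so such pairs are lost faster than pairs with one failure.

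Sensitivity: at assumed 10% v 20% failure and the same correlation, the difference goes from 10.0 to 8.1 and 5.8 points and the ratio from 2.0 to 2.16 and 2.39. At zero correlation and 5% v 15%, the ratio is 3×(1−0.05f)/(1−0.15f) = 3.08 and 3.16. The ratio is therefore nearly stable only when the two teeth of a child are unrelated.

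**Step 3. The measure and the unit.** With nothing removed and the same assumed 5% v 15%, R.R. could mean:
- absolute reduction: 0.05 − 0.15 = −10 points
- relative reduction: −0.10/0.05 = −200%
- relative risk of failure: 0.15/0.05 = 3.0
- relative risk of success: 0.85/0.95 = 0.89

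All four agree on which material does better, but not on scale.

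The unit changes the sample size. With d = 0.10 and discordant share pd = 0.0192 + 0.1192 = 0.138 (two-sided 5%, 80% power), the paired formula (1.96√pd + 0.8416√(pd − d²))²/d² gives 106.2, so 107 children. Treating teeth as independent, the pooled two-proportion formula gives 140.1, so 141 teeth per group.

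**The case against.** The strongest reply is that the removal sentence sits under Harms. Its ordinary meaning may be only that the tooth is retreated and its follow-up ends, with the failure already charted. Section 12 and the Appendix 1 column both point that way, and how removed teeth enter an analysis is often left to an SAP. Much of this stands for the secondary survival outcome. It does not settle the primary radiographic outcome, for which a tooth removed early has no 6-month film and no stated value.

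A reader might go further in four ways that the documents do not support:
- *That the plan deletes all failures and forces a null result.* Failures first seen at 6 months are recorded then, and on section 18 alone no radiograph is scheduled between baseline and 6 months.
- *That a ratio measure would be safe.* In complete pairs with correlated teeth it is inflated.
- *That the plan prescribes an unpaired analysis and so risks false positives.* Section 20 prescribes neither kind. With positively correlated teeth an unpaired analysis loses precision; it does not create false positives.
- *That R.R. is to be applied to time in minutes.* Section 20 speaks of clinical and radiographic outcomes; a method for time can be left to the SAP.

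On the unit, most of the text favours pairs, and step 11 may be loose wording for alternating materials within a child. The sentences still conflict as written.

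**Conclusion.** The point holds in a limited form. The protocol removes failed teeth without saying that they count as failures, in tension with its own survival definition. If that removal is applied to the analysis, early failures are lost, the absolute difference shrinks and the relative risk grows. On the assumed 5% v 15% with correlation 0.3, losing 25% to 50% of failures turns 10.0 points into 7.9 to 5.5, and 3.0 into 3.4 to 3.9. These sizes rest on assumed rates, an assumed correlation and equal removal with both materials; the actual bias cannot be stated. How far the primary outcome is exposed turns on the unresolved 3-month radiograph.

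Separately, and without any assumption, section 20's measure does not identify one quantity or event, and the allocation unit is contradictory. These should be corrected before data are seen. Confidence is moderate, because the removal wording has an innocent reading.

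**What to change.** 1. State that a tooth removed from the trial after pulpotomy failure is counted as a failure in the 6-month analysis. This is an analysis rule only; retreatment is unchanged. Its cost is that the radiographic primary outcome becomes partly composite, so report how many such failures were clinical only.
2. Replace the R.R. sentence with one named measure of failure at 6 months, with its direction (collagen v Biodentine). Reconcile the primary outcome first: the section 7 table has internal resorption only, section 12 has radiolucency with internal and external resorption, and Appendix 1 labels the clinical findings primary and the radiographic ones secondary.
3. Reconcile step 11 of section 11 and the timeline with the split-mouth description, and base the sample size and the comparison on within-child pairs. Both teeth of a child must then be evaluable.
4. Reconcile the 3-month radiograph between section 18, the timeline and Appendix 1.

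This takes a few sentences of protocol text. The specific interval and test, and the method for time in minutes, can stay with the SAP.
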